# 10.3 Case Report Form Items to Be Treated as Source Data

Not applicable

# 10.4 Data to Be Collected by the Sponsor

- 1) CRFs (data following acquisition of informed consent)
- 2) Copies of reports on results of drug concentration measurement
- 3) Results of clinical laboratory tests, microbiological examination, toxin A/B test, and drug sensitivity test
- 4) Copies of 12-lead ECG charts

# 11 Statistical Analysis

Details of the planned statistical analysis will be presented in the Statistical Analysis Plan (SAP).

# 11.1 Statistical Analysis Sets

# 11.1.1 Safety Analysis Set

The safety analysis set (SS) includes all patients who received the IMP at least once and from whom data on at least one safety endpoint was obtained after the start of IMP administration.

# 11.1.2 Full Analysis Set

The full analysis set (FAS) includes all patients who received the IMP at least once and from whom data on at least one efficacy endpoint was obtained after the start of IMP administration.

# 11.1.3 Microbiological per Protocol Set

The microbiological per protocol set (MPPS) comprises those patients in the FAS for whom the causative pathogen is identified and for whom microbiological outcome is assessed as "Excellent", "Good", or "Poor" according to the Assessment Criteria of Microbiological Outcome (Table 3.3-2), excluding patients for whom microbiological outcome is assessed as "Unknown/indeterminate".

#### 11.1.4 Clinical per Protocol Set

The clinical per protocol set (CPPS) comprises those patients in the FAS for whom all scheduled examinations at all specified observation time points up until the end of treatment or withdrawal have been performed.

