#### 9.2 Criteria and Procedures for Withdrawal of Individual Patients

In any of the events listed below, the investigator or subinvestigator will discontinue IMP administration, perform the tests to be performed at withdrawal stipulated in Section 7.1, Schedule and Procedures of the Trial, and promptly inform the sponsor of the withdrawal (Annex, Emergency Contact). The investigator or subinvestigator will record the date and reason for withdrawal in the source documents and CRF.

If withdrawal is necessitated by problems with safety, such as the occurrence of an AE or aggravation of the underlying disease, the investigator or subinvestigator will promptly take appropriate measures and perform follow-up if necessary (refer to Section 8.4 Follow-up Investigation of Adverse Events).

- 1. If the patient wishes to withdraw
- 2. If it is found after the start of the trial that the patient did not meet all the inclusion criteria or fell under any of the exclusion criteria
- 3. If a drug or therapy from either item 1 or item 7 in the list of prohibited concomitant drugs and therapies is used or judged to be required
- 4. If an AE making continuation of trial participation difficult occurs
- 5. If the female patient is found to be pregnant
- 6. If symptoms of the primary disease exacerbate, and the investigator or subinvestigator judges that it is not appropriate to continue the trial participation
- 7. If it becomes impossible to comply with the protocol for any another reason or if the investigator or subinvestigator judges that it is necessary to discontinue the trial participation for any another reason

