### 11.2 Handling of Data

Baseline values are defined as the last non-missing values at screening or before IMP administration. No imputation will be performed for missing data. If a problematic patient or data are encountered, the sponsor will decide how to handle the patient or data, with advice from the expert, as necessary.

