# 11.3.2 Demographic and Other Baseline Characteristics

#### 1) Endpoints

Country, race, age, sex, height, body weight, BMI, inpatient/outpatient, previous medical history, complications, diagnostic method for CDI (CDI group only), history of CDI (CDI group only), concomitant drugs, and clinical symptoms

2) Analysis Sets

SS, FAS, MPPS, and CPPS

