**CPPS** 

3) Analysis Method

Analysis will be performed by disease group and by dose, by causative strain, and by MIC values of OPS-2071 against the causative strain. Calculate frequency distribution at each evaluation time point and prepare a list of causative strains by patients.

Calculate the clinical response rate and 95% CI at each evaluation time point. Clinical response rate will be calculated as the proportion of the patients judged as "clinical cure" or "clinical improvement" against evaluable patients except for those with missing data.

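### No efficacy endpoint is analysed on the full analysis set, and early clinical failures may drop out of the end-of-treatment response rate

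*Protocol*

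**What the plan says.** Section 11.1.2 defines the FAS as "all patients who received the IMP at least once and from whom data on at least one efficacy endpoint was obtained" after dosing began. Section 11.3 names the FAS in two places: demographic and baseline characteristics (Section 11.3.2, sets "SS, FAS, MPPS, and CPPS") and treatment period (Section 11.3.3). Neither is an efficacy analysis.

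The efficacy endpoints are assigned as follows.

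| Endpoint | Section | Analysis set |
|---|---|---|
| Microbiological outcome | 11.3.4.1 | MPPS |
| Toxin A/B | 11.3.4.2 | MPPS (CDI group) |
| Clinical response | 11.3.4.3 | CPPS |
| Recurrence of CDI | 11.3.4.4 | CPPS, clinical cures only |
| Time to resolution of diarrhea | 11.3.4.5 | CPPS |
| Clinical symptoms | 11.3.4.6 | CPPS |
| Drug sensitivity | 11.3.4.7 | Isolated strains |

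Section 11.1.4 limits CPPS to FAS patients "for whom all scheduled examinations at all specified observation time points up until the end of treatment or withdrawal have been performed". Section 11.3.4.3 calculates the clinical response rate at each evaluation time point "against evaluable patients except for those with missing data", and Section 11.2 adds: "No imputation will be performed for missing data".

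One of the Section 9.2 withdrawal criteria is worsening disease: "If symptoms of the primary disease exacerbate, and the investigator or subinvestigator judges that it is not appropriate to continue the trial participation". Another is use of, or need for, other treatment for CDI or enteric infection.

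**The concern.** Efficacy is a primary objective, yet no efficacy rate is planned over all treated patients who have efficacy data. Two features of the set that is used cause trouble.

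First, CPPS membership depends on completing every scheduled examination. Table 7-1 schedules laboratory tests, ECG, vital signs, a plasma sample and stool specimens alongside the clinical assessment. Missing any one of them says little about clinical response but, on the literal definition, removes the patient. With 10 patients per dose and disease group, each removal matters.

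Second, a poor course can lead to withdrawal, and the end-of-treatment rate has no rule that keeps withdrawn patients in. If early failures are lost, the rate describes patients who did well enough to reach end of treatment. It is then too high, and by more at a dose where more patients fail early. The rates by dose are the product of this descriptive trial, so their denominators need to be right.

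**Working it through.** **1. What happens to a patient withdrawn for failure during dosing?** The relevant sections, side by side:

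- Section 11.1.4 requires examinations only up to end of treatment or withdrawal. A patient withdrawn early with everything done to that point remains in CPPS.
- Sections 7.1.7.1, 7.1.7.2 and 7.2.2.3 schedule a clinical response assessment at withdrawal during dosing.
- Table 3.3-3 classes a patient already given other treatment for CDI or enteric infection as a clinical failure.

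Such a patient is therefore normally in CPPS with a recorded outcome. Two routes out of the end-of-treatment rate remain:

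- (a) Section 7.1.7 lets the withdrawal examination be partial on refusal or in an emergency, and gives an SAE and CDI recurrence as examples. A partial examination can fail the CPPS condition.
- (b) Table 7-1 shows withdrawal as its own column. The assessment method in Section 7.2.2.3 names only Day 4 and end of treatment, and Section 11.3.4.3 reports by time point. Nothing places a withdrawal assessment at end of treatment, so it can be treated as missing there and dropped.

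**2. Size.** The protocol's figure of 60 patients reproduces: 3 doses × 2 disease groups × 10 = 60. It gives no response or withdrawal rate, so the counts below are assumptions. All 10 patients in a cell are taken to be in the FAS.

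Let x be the number of responders and k the number of withdrawn failures lost.

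- FAS rate, lost patients counted as non-responders: x/10
- Rate with lost patients dropped: x/(10 − k)

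For x = 7, with exact (Clopper-Pearson) 95% intervals:

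| k | Rate | 95% CI |
|---|---|---|
| 0 | 7/10 = 70% | 34.8 to 93.3% |
| 1 | 7/9 = 77.8% | 40.0 to 97.2% |
| 2 | 7/8 = 87.5% | 47.3 to 99.7% |
| 3 | 7/7 = 100% | 59.0 to 100% |

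Range over other response counts:

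- x = 6, k = 0 to 3: 60%, 66.7%, 75.0%, 85.7%
- x = 8, k = 0 to 2: 80%, 88.9%, 100%

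Across these cases each further lost failure adds between 6.7 points (60% to 66.7%) and 12.5 points (87.5% to 100%). At k = 0 nothing changes.

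**3. Dose comparison.** Suppose one dose has 8/10 responders with none lost, and another has 6/10 with two failures lost. The FAS difference is 80 − 60 = 20 points. The reported difference is 80 − 75 = 5 points. This needs early failure to be more frequent at the weaker dose, which is again an assumption.

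**4. Recurrence.** The CPPS condition ends at end of treatment, so a missed follow-up visit does not remove anyone. Recurrence is also assessed at withdrawal after dosing (Section 7.1.7.1). What remains is that the denominator starts from CPPS rather than FAS, and patients with missing recurrence status are dropped.

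**The case against.** The strongest objection is that failures are not automatically lost. The CPPS definition itself allows for withdrawal, a response is scheduled at that visit, and other treatment counts as failure. This stands. A reader might infer from the CPPS restriction and the missing-data rule that every patient withdrawn for failure disappears from the rate. The documents do not support that: loss requires an incomplete examination, or a withdrawal assessment that is not counted at end of treatment.

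It can also be said that visit mapping is normally left to the SAP, to which Section 11 defers details. That is fair for route (b), which an SAP could close. It does not answer the choice of set and denominator. Section 11.3.4 fixes both, and Section 11.4 treats departures from the protocol's method as deviations to be explained.

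A reader might multiply assumed completion rates over all scheduled items to predict how far CPPS shrinks. The documents give no completion rates, and items at one visit tend to be missed together, so no attrition figure is offered here. It is also arguable that scheduled examinations in Section 11.1.4 was meant more narrowly, but the protocol does not say so.

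Finally, a reader might infer that the decision on whether 100 mg is effective is biased in the same way. Section 3.2 leaves the Data Review Committee's procedures to a separate document, and nothing ties its review to CPPS.

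**Conclusion.** The point holds in conditional form. No efficacy endpoint uses the FAS. CPPS, read literally, excludes patients for missed examinations unrelated to efficacy, and missing outcomes are dropped without imputation. Early failures may therefore leave the end-of-treatment denominator, though they need not.

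If they do, the assumed example of 7 responders among 10 moves from 70% to between 77.8% and 100% as one to three failures are lost. If none is lost, there is no bias from this source. The actual number cannot be predicted from the protocol.

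This is a should-fix: the trial is small and descriptive, with no hypothesis test and a sample size not set by statistical methods. The exclusion of patients whose microbiological outcome is unknown from MPPS (Section 11.1.3, "excluding patients for whom microbiological outcome is assessed as" unknown/indeterminate) is a separate, stated choice and is left as it is.

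**What to change.** Change the wording of Sections 11.1.4, 11.2 and 11.3.4 as follows.

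- **Clinical response (11.3.4.3):** make the FAS the main set. Count the assessment at withdrawal during dosing as the end-of-treatment response. Count FAS patients with neither an end-of-treatment nor a withdrawal assessment as non-responders, and adapt Section 11.2 to allow this. Report how many treated patients fall outside the FAS for lack of any efficacy data.
- **CPPS (11.1.4):** keep it as a supportive set, requiring the clinical response assessment rather than every scheduled examination.
- **Recurrence (11.3.4.4):** use FAS patients with clinical cure at end of treatment, report the number with missing recurrence status, and add a sensitivity analysis counting them as recurrent. State whether a cure recorded at withdrawal during dosing admits a patient to this denominator, since no recurrence assessment is scheduled in that case.

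No new data are needed. The cost is a protocol wording change and somewhat lower reported response rates.

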#### 11.1.5 Pharmacokinetics Analysis Set

The pharmacokinetics analysis set (PKS) comprises patients in whom plasma drug concentration was measured at least once.

### 11.2 Handling of Data

Baseline values are defined as the last non-missing values at screening or before IMP administration. No imputation will be performed for missing data. If a problematic patient or data are encountered, the sponsor will decide how to handle the patient or data, with advice from the expert, as necessary.

#### 11.3 Analysis Items and Method

#### 11.3.1 Safety Analysis

#### 1) Endpoints

Adverse events, clinical laboratory tests, vital signs (body temperature, blood pressure and pulse rate), 12-lead ECG

2) Analysis Set

SS

#### 3) Analysis Method

Analysis will be performed for the entire study population and by disease group and by dose. AEs that occurred after the start of treatment with IMP will be tabulated using MedDRA by System Organ Class (SOC) and Preferred Term (PT), with PT substituted for verbatim terms. The number of patients who experienced the following events as well as and the incidence will be tabulated: adverse events, adverse drug reactions, serious adverse events, adverse events leading to withdrawal, and adverse events by severity.

Clinical laboratory tests and vital signs (body temperature, blood pressure, and pulse rate) will be analyzed by using frequency distributions and descriptive statistics.

Regarding 12-lead ECG, a shift table will be prepared for judgment on abnormality at each time point before and after IMP administration.

# 11.3.2 Demographic and Other Baseline Characteristics

#### 1) Endpoints

Country, race, age, sex, height, body weight, BMI, inpatient/outpatient, previous medical history, complications, diagnostic method for CDI (CDI group only), history of CDI (CDI group only), concomitant drugs, and clinical symptoms

2) Analysis Sets

SS, FAS, MPPS, and CPPS

#### 3) Analysis Method

Analysis will be performed by disease group and by dose. Frequency distribution or descriptive statistics for each variable will be calculated according to the nature of the data (continuous or discrete).

Protocol No. 341-13-002

#### 11.3.3 Treatment Period

1) Endpoints

Number of days when IMP was administered, total dose, total number of administrations

2) Analysis Sets

SS, FAS, and CPPS

3) Analysis Method

Analysis will be performed by disease group and by dose. Descriptive statistics will be calculated for number of days when IMP was administered, total dose, and total number of administrations.

#### 11.3.4 Efficacy Analysis

#### 11.3.4.1 Microbiological Outcome

1) Endpoints

Bacteria elimination rate

2) Analysis Set

**MPPS** 

3) Analysis Method

Analysis will be performed by disease group and by dose, and by MIC values of OPS-2071 against the causative strain. The number and proportion of patients by causative strain, a list of causative strain by patient, and a list of the result based on bacterial culture at each evaluation time point will be prepared.

Concerning microbiological outcome by causative strain, bacteria elimination rate and its 95% CI will be calculated. The bacteria elimination rate is the proportion of causative strains assessed as either "excellent" or "good" except for those assessed as "Unknown/indeterminate". In case of infection of multiple bacteria, assess the microbiological outcome of each infections agent.

# 11.3.4.2 Toxin A/B Assay (Clostridium Difficile Infection Group Only)

1) Endpoint

Toxin positive rate

2) Analysis Sets

MPPS (CDI group only)

3) Analysis Method

Analysis will be performed by dose. Based on the result of Toxin A/B assay performed by the microbiological laboratory, prepare a list on the result of positive/negative judgment in the Toxin A/B assay at each evaluation time point.

Calculate Toxin A/B positive rate and its 95% CI. Toxin A/B positive rate is the proportion of the number of Toxin positive patients against the number of evaluable patients in CDI group.

Toxin positive rate (%) = 
$$\frac{\text{Number of toxin positive patients}}{\text{Number of patients assessed for microbiological outcome}} \times 100$$

# 11.3.4.3 Clinical Response

1) Endpoint

Clinical response

2) Analysis Set

**CPPS** 

3) Analysis Method

Analysis will be performed by disease group and by dose, by causative strain, and by MIC values of OPS-2071 against the causative strain. Calculate frequency distribution at each evaluation time point and prepare a list of causative strains by patients.

Calculate the clinical response rate and 95% CI at each evaluation time point. Clinical response rate will be calculated as the proportion of the patients judged as "clinical cure" or "clinical improvement" against evaluable patients except for those with missing data.

# 11.3.4.4 Recurrence of *Clostridium Difficile* Infection (*Clostridium Difficile* Infection Group Only)

1) Endpoint

CDI recurrence rate

2) Analysis Set

**CPPS** 

3) Analysis Method

Analysis will be performed by dose in the proportion of patients judged as "clinical cure" at the end of treatment in CPPS.

Prepare the list of result of judgment on CDI recurrence at FU2 or withdrawal.

Calculate CDI recurrence rate at FU2 or withdrawal. CDI recurrence rate is the proportion of the patients judged as "recurrent" against evaluable patients except for those with missing data.

Recurrence rate (%) = 
$$\frac{\text{Patients judged as "recurrent"}}{\text{Evaluable patients except for those with missing data}} \times 100$$

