#### Secondary objectives:

- To assess the recurrence rate of CDI in patients with bacterial enteritis associated with CDI after multiple doses of OPS-2071.
- To assess the time to resolution of diarrhea in patients with bacterial enteritis associated with CDI or enteric infection after multiple doses of OPS-2071.
- To assess the improvement of clinical symptoms in patients with bacterial enteritis associated with CDI or enteric infection after multiple doses of OPS-2071.
- To assess the sensitivity to OPS-2071 of the causative pathogen strain isolated from patients with bacterial enteritis associated with CDI or enteric infection.

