# 3.3.2.4 Recurrence of *Clostridium Difficile* Infection (*Clostridium Difficile* Infection Group Only)

The investigator or subinvestigator will assess the recurrence of CDI at FU2 or withdrawal according to the assessment criteria shown in Table 3.3-4 for patients who achieved "clinical cure" at the end of treatment.

Table 3.3-4 Assessment Criteria for Recurrence of *Clostridium Difficile* Infection

Assessment of Recurrence of CDI	Definition
Sustained cure	No recurrence
Recurrence	
 
Meeting all the following criteria
 
New episode of diarrhea is occurred in the period from the end of treatment to FU2 or withdrawal (liquid or unformed stools ≥ 3 times/day within 24 hours)
 

	Medication or therapy is required to treat CDI in the period from the end of treatment to FU2 or withdrawal
	A positive toxin A/B assay at FU2 or withdrawal (positive for either or both toxins)

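### The CDI recurrence rate is taken only among patients cured at end of treatment, and no rate of cure lasting to Day 38 over all treated CDI patients stands beside it

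*Protocol*

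**What the plan says.** The secondary objective covers CDI patients in general, with no restriction to those cured: "To assess the recurrence rate of CDI in patients with bacterial enteritis associated with CDI after multiple doses of OPS-2071".

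The assessment and the analysis are narrower. Section 3.3.2.4 has recurrence judged at follow-up 2 (FU2, Day 38) or withdrawal only "for patients who achieved 'clinical cure' at the end of treatment". Section 11.3.4.4 repeats the restriction: "Analysis will be performed by dose in the proportion of patients judged as 'clinical cure' at the end of treatment in CPPS". It then defines the rate: "CDI recurrence rate is the proportion of the patients judged as 'recurrent' against evaluable patients except for those with missing data". The CPPS is itself a subset of the FAS, limited to patients "for whom all scheduled examinations at all specified observation time points up until the end of treatment or withdrawal have been performed".

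Table 3.3-4 has a category "Sustained cure", defined as no recurrence and so the complement of recurrence within the cured subset. No part of section 11.3.4 turns it into a proportion. The nearest other clinical rate is in section 11.3.4.3: "Clinical response rate will be calculated as the proportion of the patients judged as 'clinical cure' or 'clinical improvement' against evaluable patients". That rate pools cure with improvement, and clinical response is not assessed after the end of treatment.

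**The concern.** Being cured at Day 11 is itself a result of the dose. The denominator of the recurrence rate can therefore differ between doses in both size and type of patient. A weaker dose may retain only patients who were easy to cure and who may also relapse less. A stronger dose adds harder cases to its own denominator. A patient not cured at end of treatment cannot count against a dose in this rate. A patient rated as improved counts as a responder in section 11.3.4.3, yet cannot be counted as recurrent in section 11.3.4.4.

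This is a dose-ranging trial meant to give exploratory information on the recommended dose, and section 3.2, item 4, presents recurrence as the main difficulty in treating CDI. The doses will be read side by side on this figure, and it can order them differently from the proportion of treated patients who are cured and stay cured.

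**Working it through.** **Inputs from the protocol.** There are 10 CDI patients per dose and three doses (section 3.4). Recurrence after metronidazole or vancomycin is about 15% to 30% (section 3.2, item 4). The protocol gives no cure rate by dose and no target for recurrence or sustained cure, so the cure rates below are assumptions.

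**The plan's own figure.** The only related stated figure is the sample size in section 11.5. CDI: 10 evaluable / 1.0 detection = 10. Enteric infection: 5 evaluable / 0.5 = 10. (10 + 10) × 3 doses = 60, which reproduces the stated 60.

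**Two rates from the same patients.** Let c be the number cured at end of treatment and r the number who recur, out of n = 10.

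- Planned recurrence rate = r / c
- Sustained cure rate = (c − r) / n

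| Assumed counts | r / c (exact 95% CI) | (c − r) / 10 (exact 95% CI) |
|---|---|---|
| Dose A: c = 5, r = 0 | 0/5 = 0% (0 to 52) | 5/10 = 50% (19 to 81) |
| Dose B: c = 10, r = 2 | 2/10 = 20% (3 to 56) | 8/10 = 80% (44 to 97) |

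A looks better on the planned rate and B on sustained cure.

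**A case-mix illustration (all values assumed).** Suppose 60% of patients are easy to cure with 10% recurrence, 30% are harder with 40% recurrence, and the rest are not cured by either dose.

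- Dose curing only the easy cases: recurrence 10%; sustained cure 0.6 × 0.9 = 54%.
- Dose curing both kinds: recurrence (0.6 × 0.1 + 0.3 × 0.4) / 0.9 = 20%; sustained cure 0.54 + 0.3 × 0.6 = 72%.

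**How often the order reverses.** Independent binomial counts were enumerated exactly for two doses of 10 patients. A reversal means that the low-cure dose shows the lower observed recurrence rate but fewer sustained cures.

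| Assumed cure, low vs high dose | Same true recurrence in both (15% to 30%) | Assumed recurrence 5% (low) vs 25% (high) |
|---|---|---|
| 30% vs 90% | 46 to 49% | 76% |
| 40% vs 90% | 41 to 45% | 70% |
| 50% vs 90% | 35 to 39% | 60% |
| 60% vs 80% | 19 to 23% | 32% |

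In the equal-recurrence column the reversal comes from small denominators together with unequal cure, not from bias in the recurrence rate. For example, 4 cured patients show no recurrence with probability 0.70^4 = 24% to 0.85^4 = 52%. For 9 cured patients the range is 0.70^9 = 4% to 0.85^9 = 23%. The right-hand column adds selection of easier cases.

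**The case against.** **The rate is legitimate.** Recurrence presupposes a cure, and the protocol measures it in cured patients consistently. Recurrence among the cured and sustained cure among the treated are different quantities, and differing orders do not make either one wrong. This stands. A reader might infer that the planned rate is an error, but the documents do not support that.

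**Much can be reconstructed.** Section 11.3.4.3 plans a frequency distribution of clinical response by dose, and section 11.3.4.4 a list of recurrence judgments. The cured counts would be visible and the subtraction is simple. This stands in part: it works only for CPPS patients and is not a planned analysis.

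**Day 38 is not empty.** A reader might infer that no Day 38 result reaches beyond the cured patients. That is too broad. Laboratory tests, vital signs and adverse events at FU2 are analysed in the safety set. Clinical symptoms (CPPS) and toxin A/B (microbiological per protocol set) at FU2 are analysed without a cure condition. What is missing is a clinical cure rate through Day 38 over all treated CDI patients.

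**The stakes are low.** Recurrence is a secondary objective and its assessment is called exploratory. The sample size is not statistically derived, and the Data Review Committee's dose-path decision rests on the treatment period. Intervals of 19 to 81% and 44 to 97% overlap widely, so sustained cure would not rank the doses reliably either. Only 50 mg versus 200 mg is randomised, on one path, so no choice of denominator creates a randomised comparison with 100 mg. All of this stands and limits the weight of the point.

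**The analysis plan may cover it.** Section 11 leaves details to the SAP, which was not available here and could add such a rate. However, the protocol itself fixes the endpoint, subset and formula, and the point concerns how those will be read.

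**Conclusion.** The point holds as a weakness of interpretation. The by-dose recurrence rate is conditioned on response to the dose, and the protocol pairs it with no clinical cure rate through Day 38 over all treated CDI patients. In the assumed example, 0% versus 20% recurrence goes with 50% versus 80% sustained cure. Under the assumed cure rates, such a reversal occurs in 19 to 49% of two-dose comparisons even when true recurrence is equal, and more often if the weaker dose retains easier cases.

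These sizes rest on assumed cure rates, and the case-mix effect rests on an assumed link between ease of cure and relapse. A reader might infer that the plan will lead to the wrong dose being chosen. The protocol does not support that: the reversal is possible rather than certain, and no dose decision rule uses Day 38 recurrence.

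**What to change.** Add to section 11.3.4.4 a sustained cure rate by dose with an exact 95% CI.

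- **Numerator:** CDI patients with clinical cure at end of treatment and no recurrence through FU2.
- **Denominator:** all CDI patients in the FAS. State that the FAS (section 11.1.2) also requires at least one efficacy result after the start of dosing, so it may be slightly smaller than all who received the product.
- **Not cured at end of treatment:** count as not sustained.
- **Cured, but no recurrence judgment at FU2 or withdrawal:** count as not sustained in the main figure, as an explicit exception to the no-imputation rule in section 11.2. Show the figure with these patients excluded alongside. With 10 patients per dose, classifying one patient differently moves the rate by 1/10 = 10 percentage points, so the rule should be fixed in advance.
- **Use:** read the doses side by side on this rate, descriptively, and keep the recurrence rate among cured patients as a description.

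No new data are needed, because clinical response and the recurrence judgment are already collected. The cost is analysis wording, a little more analysis work, and a headline figure less favourable than one minus the recurrence rate.
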